1.4 SUMMARY OF PHASE I CLINICAL TRIAL

1.4.1 Methods

A single-arm, open-label, phase I clinical trial was performed to evaluate the safety of PepCan in adult females with biopsy-confirmed HSIL. A dose-escalation phase has been completed in which doses of 50, 100, 250, and 500 µg/peptide/dose (6 subjects/dose level; 4 doses/subject with 3 weeks between each dose) were evaluated to determine the maximum tolerated dose (MTD), the clinically optimal dose (COD), and the immunologically optimal dose (IOD). Blood was drawn for CD3 ELISPOT (to assess CD4 and CD8 responses) and immune suppressor cell analysis before and after the second and fourth injections. HPV-DNA testing was performed before and after the four injections. Clinical response was assessed by performing LEEP excision approximately 3 months after the fourth injection. Subjects who no longer had HSILs were considered to be complete responders, and those with HSILs measuring $\leq 0.2\text{mm}^2$ were considered to be partial responders. The final dose phase in which additional 10 subjects were vaccinated at the COD dose of 50 µg/peptide/dose was also performed.

1.4.2 Accrual

At the end of the Phase I study, 52 subjects were enrolled, and 34 received the vaccine. Thirty-one subjects completed the study (mean age of 30.8 ± 6.7 years old).

1.4.4 Clinical response

The histological response rates in order of increasing doses were 50%, 50%, and 33%, and 40% (**Table 3**). The overall histological response rate was 45%, and none progressed to cervical squamous cell carcinoma. In comparison, a historical placebo group in another clinical trial of HPV therapeutic vaccine with a similar study reported a regression rate of 22% [No statistically significant differences were detected when histological response rates were compared (1) between subjects with entry diagnosis of CIN 2 versus CIN3, (2) between subjects ≤ 25 years of age versus > 25 years of age, and (3) between subjects who were HPV-16-positive versus those who were not.

The mean number of cervical quadrants with visible lesions decreased significantly from 1.9 quadrants to 0.8 quadrants after vaccination ($p=0.001$).

1.4.5 Viral clearance

At least one HPV type present at entry became undetectable in 21 of 31 (70%) patients (**Table 3**). By doses, the rates were 85%, 50%, 50%, and 40% with the highest undetectability at the lowest dose.

1.4.6 Immunological response

1.4.6.1 Systemic

Immunological responses to HPV-16 E6, as measured by IFN- γ ELISPOT assay, were similar among the first 3 dose levels in terms of detecting positive response to at least one new E6 region and for the increase in response being statistically significant (**Table 3**). The lowest response rate was observed in the 500- μ g dose level. No immunodominant HPV-16 E6 region was identified and the number of regions to which new immune responses were detected was also variable (**Fig. 3**).

Immune profiling (**Fig. 4**, upper panel) showed statistically significant increases in circulating Th1 cells after 2 ($p=0.02$) and 4 vaccinations ($p=0.0004$). Th2 cells initially increased significantly ($p=0.01$) but decreased to below baseline level after 4 vaccinations, although not significantly. Treg levels were minimally changed. The differences in Treg levels prevaccination ($p=0.03$) and post-2 vaccinations ($p=0.04$) between these two groups were statistically significant (**Fig. 4**, lower panel).

Fig. 3 HPV 16 E6- and E7-specific CD3 T-cell responses before vaccinations, after 2 vaccinations, and after 4 vaccinations. T-cell lines were established by stimulating CD3 T-cells with autologous dendritic cells pulsed with HPV 16 E6-vac, E6-GST, E7-vac, and E7-GST. Samples from different visits were tested with overlapping peptides in the same ELISPOT assay, and each region was tested in triplicate. Results are shown for subjects with statistically significant increases to the E6 peptides, and the regions with significant increases (paired *t*-test) are marked by “*”. Subjects 4 and 11 also had a significant increase to E7 (marked by “e”), which may represent the first examples of

[figure not shown]

Table 3. Summary of results from the dose-escalation Phase I clinical trial

Characteristics\Dosage (n)	50 µg (14)	100 µg (6)	250 µg (6)	500 µg (5)	All (31)
Histological regression, % (n)					
Responders	50 (7)	50 (3)	33 (2)	40 (2)	45 (14)
Virological response ^{a,b} , % (n)					
Responders	85 (11)	50 (3)	50 (3)	40 (2)	70 (21)
Immunological response, % (n)					
New response ^c to HPV-16 E6	64 (9)	67 (4)	83 (5)	20 (1)	61 (19)
Significant response ^d to HPV-16 E6	43 (6)	50 (3)	50 (3)	20 (1)	42 (13)

[figure not shown]
a At least one HPV type detected at entry became undetectable at exit

b One subject had no HPV detected at entry in the 50 µg group

c New response was detected after vaccination but not prior to initiation of vaccination

d Significant response had $p < 0.05$ using Student's *t*-test comparing values before and after vaccination

[figure not shown]
Fig. 4 FACS analysis of peripheral immune cells. The upper panel show systemic Th1, Th2, and Treg before, after 2, and after 4 vaccinations. In the lower panel, responders are indicated by filled circles while non-responders are indicated by filled squares. None of the subjects with prevaccination Treg levels $\geq 0.7\%$ was a vaccine responder. Cells were first stained with antibodies for surface markers CD3, CD4, and CD25. Staining for intracellular T-bet, GATA3, and Foxp3 was performed with the Foxp3 staining kit according to the manufacturer's instructions (eBioscience). Th1 cells were expressed as a percentage of CD4 cells positive for T-bet, Th2 cells as a percentage of CD4 cells positive for GATA3, and Treg cells as a percentage of CD4 cells positive for CD25 and Foxp3. Paired *t*-test (upper panel) or Wilcoxon rank-sum test (lower panel) was used.

1.4.6.2 Cervical

In the cervix, the number of Tregs were lower in histological responders in the epithelium and the underlying stroma, but not significantly (Fig. 5).

Fig. 5 Regulatory T-cells in lesional cervical epithelium and the underlying stroma. FoxP3 nuclear staining cells, in lesions (cervical intraepithelial neoplasia 1, 2, and/or 3) remaining after vaccination or representative region if no lesions remaining, were counted. The FoxP3 staining cells were also counted in the underlying stroma. The bars represent stand error of means.

1.5 RATIONALE FOR PHASE II CLINICAL TRIAL

1.5.1 Need for HPV Therapeutic Vaccines

Although numerous preclinical and clinical trials have evaluated prophylactic HPV vaccines during the past few decades, these vaccines do not help those who already have established HPV infections [51]. Gardasil, a quadrivalent HPV L1 virus-like particle prophylactic vaccine (HPV types 16, 18, 6, and 11), was the first to be FDA-approved in 2006; a bivalent version (HPV types 16 and 18), Cervarix, was approved by the FDA three years later. Clinical trials have demonstrated excellent vaccine efficacy in women negative for HPV 16 or HPV 18[52, 53], but the duration of protection remains to be determined, and a study of the bivalent vaccine showed no evidence of enhanced viral clearance in women with pre-existing HPV infections (n=1,259; 35.5% clearance in vaccinated group, 31.5% in a group receiving a negative control vaccine, $p=NS$) [51]. Therefore, therapeutic vaccines are needed for cases in which HPV infection is already established and in which HPV-related diseases have already developed. This is the particularly true because the prophylactic vaccine coverage rate in the targeted group (girls aged 13–17 years) has been reported to be only 32% nationally [54]. Although the standard surgical treatments for HSILs such as LEEP are very effective [14], their unintended side effect of increased incidence of preterm delivery from 4.4% to 8.9% [14, 15] has become a concern. Henceforth, the latest guideline no longer recommends treatment for CIN2 in young women (narrowly defined as ≤ 24 years old and broadly defined as any women who still plans to become pregnant [14]). Treatment is still recommended for CIN3 but observation is now considered acceptable. A new treatment, which does not alter the anatomical integrity of the cervix like the HPV therapeutic vaccine, is very much needed. In short, **HPV therapeutic vaccines are needed** because (1) prophylactic vaccines are not effective against established HPV infection, (2) utilization of the prophylactic vaccines has been low, (3) therapeutic vaccines would leave the cervix intact and would likely not increase the risk of preterm deliveries, and (4) therapeutic vaccine maybe effective against other cancers caused by HPV such as anal, oropharyngeal, penile, vaginal, and vulvar cancers.

1.5.2 Rationale for Proposed Dose of HPV Peptides

In the Phase I clinical trial, four dose levels (50, 100, 250, and 500 µg per peptide) were tested. These four dose levels were chosen based on information available in the literature. Published studies of clinical trials using various peptide vaccines reported using doses that range from 5–3,000 µg per peptide [31–38]. Optimal doses (and smaller doses if two dose levels were the same) for achieving immunogenicity differed greatly among the vaccines: 30 µg of 96-mer malaria peptide [31], 500 µg of 9-mer peptide for treating prostate cancer [34], 50 µg each of 13 HPV 16 E6 and E7 peptides ranging from 25 to 35 amino acids long [35]. Therefore, the dose levels likely to elicit the optimal immunogenicity were chosen.

The dose-escalation portion of the Phase I clinical trial has demonstrated that the 50 µg/peptide/injection was optimal in terms of histological regression, viral clearance, and vaccine-induced immune responses (**Table 3**). Therefore, this dose will be used for the Phase II clinical trial.

1.5.3 Rationale for Proposed Dose of Candin®

Three hundred (300) µL of Candin® will be administered per injection, which was the amount used for intralesional injection of warts [47, 55], as well as the amount of Candin® as a vaccine adjuvant in the Phase I clinical trial. The same amount will be used for the Phase II clinical trial as this amount has been shown to be safe and effective.

1.5.4 Rationale for Proposed Route of Injections

Intradermal route of administration will be used to make use of LCs as antigen-presenting cells. A Phase I clinical trial of a peptide vaccine for prostate cancer administered through this route has shown promising immunogenicity [34]. This route has also been shown to be safe, effective, and immunogenic in the Phase I clinical trial, and will be used for the Phase II clinical trial.

1.5.5 Rationale for Proposed Site of Injections

Extremities have been chosen as the site of administration because of the ease of access as well as availability of sufficient data demonstrating efficacy of HPV peptides delivered at these sites [35, 56]. As injecting in limbs has shown to be safe, effective, and immunogenic in the Phase I clinical trial, the same sites will be used for injection in the Phase II clinical trial.

1.5.6 Rationale for Number of Injections

In published studies of peptide vaccines, the total number of injections ranged from 2 to 17 [31–38]. We proposed to use four injections because Hueman et al. demonstrated that immunogenicity peaked after four injections (six injections in total were given in the study) [34], and four injections appeared to be sufficient in the Phase I clinical trial.

1.5.7 Rationale for Interval between Injections

The interval between injections ranged from 2 weeks to 90 days in the published studies [31–38], but most used a 3-week interval. Kenter and colleagues reported that peptide vaccine immunogenicity measured by IFN-γ ELISPOT assay was less prevalent when blood samples were drawn 7 days after the last vaccination but was higher when they were drawn 3 weeks after the last vaccination [35]. Therefore, we chose the 3-week (± 7 days) interval because it appears to be long enough to allow sufficient mounting of immune responses. As this interval has been shown to be safe, effective, and immunogenic, the same interval will be used in the Phase II clinical trial.

1.5.8 Rationale for Interval between the Last Injection and Final Histologic Assessment

While histological response was assessed 3 months after the last vaccination by performing LEEP in the Phase I clinical trial, the full effect is known to take 1 year [17-19]. In the Phase II clinical trial, PepCan will be administered as an alternative to LEEP, and histological response will be assessed by obtaining colposcopy-guided quadrant biopsies 12 months after the last injection (Fig. 6). In a clinical trial which used a similar peptide-based HPV therapeutic vaccine to treat high-grade vulvar intraepithelial lesions, histological regression increased from 25% to 47% between 3 months and 12 months post-vaccinations [18].

1.5.9 Rationale for Primary Outcome Measure: Efficacy

The clinical response to evaluate the vaccine efficacy will be assessed by comparing the punch biopsy results between the Screening Visit (having had HSIL to qualify for vaccination) and the 12-Month Visit (\pm 2 weeks) (Fig. 6). LEEP will not be performed to assess efficacy, but it will be offered at no cost to subjects who have persistent HSILs at the 12 Mo Visit.

The design of the proposed Phase II trial is single-site, and randomized to 2 treatment arms in a double-blinded fashion. We will use a historical placebo group from a clinical trial with similar design (i.e., enrollment of subjects with biopsy-proven CIN2/3, and clinical response assessed by biopsy in 15 month) for comparison [57]. The overall histological regression rate in the dose-escalation Phase I clinical trial was 52% three months after the last vaccination, and this is expected to substantially increase with an extended 12-month observation period.[18] Assuming a conservative rate of 60%, n=35 in the PepCan arm would give 91% power (two-tailed, $\alpha=0.05$) for detecting a statistically significant difference from the historical placebo group which had a 29% (34 of 117) regression rate [57]. Although there is greater uncertainty regarding the Candin®-only arm, there is $\geq 90\%$ power to detect a significant differences between the PepCan and Candin® arms under multiple plausible scenarios (for example, regression rates of 67% vs. 29%, or 85% vs. 50%). Forty subjects in each arm will be enrolled to ensure that at least 35 subjects in each would complete the study. While the use of historical placebo group is not as rigorous as having a concurrent placebo group, a concurrent placebo group with biopsy-proven CIN2/3 that would go untreated for 12 months would be difficult to ethically justify.

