1.5.13 Rationale for Adding a Candin® Arm

The results of the dose-escalation portion of the Phase I clinical trial showed similar rates of clinical responses in subjects with HSILs associated (4 of 9 or 44%) and not associated (8 of 14 or 57%) with HPV 16 suggesting that *de novo* immune stimulation presumably from Candin® plays a major role. Therefore, Candin® only treatment arm will be added to compare efficacy between PepCan and Candin®.

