2 OBJECTIVES

2.1 PRIMARY OBJECTIVE: EFFICACY

To assess the efficacy of PepCan and Candin® in a Phase II clinical trial by determining clinical response which will be assessed by obtaining colposcopy-guided quadrant biopsies at the 12-Month Visit. Responses will be compared between (1) the PepCan group and a historical placebo group [57], (2) the Candin® group and the same historical placebo group, and (3) the PepCan and Candin® groups. If, upon the 12-Month Visit quadrant biopsies, a subject does not have any evidence of CIN, she would be considered a “complete responder”. If the lesion(s) has(have) regressed to CIN 1, the subject will be considered to be a “partial responder”. If there is still CIN 2 and/or 3 present at the 12-Month Visit, the subject will be considered a “non-responder”. The highest grade among the biopsies will be recorded. In addition to the above analysis of subjects who exited after the 12-Month Visit, another analysis may be performed with addition of subjects who exited the study after the 6-Month Visit if histological results (biopsy and/or LEEP) are available at 6 months.

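### The stated power of at least 90% for PepCan vs Candin holds only at PepCan rates above the 60% used in the same paragraph; at 60% vs 29% it is 74% by chi-square or 66% by Fisher with 35 per arm

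*Protocol*

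**What the plan says.** Protocol section 2.1 lists three comparisons under the primary efficacy objective. Two are against a historical placebo group. The third compares "3) the PepCan and Candin® groups" with each other, and it is the only one based on randomisation.

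Section 1.5.9 gives the sample size reasoning. For the historical comparison: "Assuming a conservative rate of 60%, n=35 in the PepCan arm would give 91% power", against "the historical placebo group which had a 29% (34 of 117) regression rate". The next sentence turns to the two arms. It opens "Although there is greater uncertainty regarding the Candin®-only arm" and then puts the power of the between-arm comparison at 90% or more. The rates behind that claim are given by way of example: "under multiple plausible scenarios (for example, regression rates of 67% vs. 29%, or 85% vs. 50" (percent). Forty per arm are enrolled so that at least 35 per arm complete.

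Neither document fixes a planning rate for Candin. Section 1.5.13 adds the Candin arm because Phase I responses were similar in HPV 16 and non-16 lesions, which it takes to suggest that "immune stimulation presumably from Candin® plays a major role". It gives no number for that role.

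The between-arm test is Fisher's exact test in Protocol section 9.1 and Pearson's chi-square in SAP section II.c.

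**The concern.** The paragraph uses one PepCan rate for the historical comparison and higher ones for the randomised comparison. In the first between-arm scenario PepCan rises to 67% and Candin stays at the placebo rate, so Candin does nothing. In the second Candin is allowed 50%, but PepCan rises to 85%, which is 25 points above 60%. No scenario pairs the 60% rate with any Candin rate.

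The difference between the arms is the contribution of the peptides alone. Both scenarios set it at 35 to 38 points. The section's own rates imply a total effect over placebo of 31 points, to be shared between peptides and Candin. If Candin contributes something, as section 1.5.13 expects, the peptide share at those rates is smaller still.

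What is at stake is how a null result is read. A reader told that this comparison has at least 90% power could take a non-significant result as good evidence that the peptides add nothing.

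**Working it through.** **Inputs.** From section 1.5.9: 35 completers (40 enrolled) per arm; PepCan 60%, 67% and 85%; Candin 29% and 50%; historical rate 34 of 117. Allocation is 1:1 (section 4.2). The two-sided 0.05 level is stated for the historical comparison and assumed to carry over. A Candin rate of 40% is an assumption, added as an intermediate value.

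**Method.** Exact power: for every pair of responder counts, compute the two-sided p-value, keep the pairs with p ≤ 0.05, and sum their binomial probabilities. Cross-check by the pooled normal approximation:

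power = Φ{ [ |p1 − p2| − 1.96·√(2p̄(1 − p̄)/n) ] / √([p1(1 − p1) + p2(1 − p2)]/n) }, with p̄ = (p1 + p2)/2.

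**Step 1: reproduce the plan.** For 67% vs 29%, n = 35, p̄ = 0.48:
- 1.96·√(2 × 0.48 × 0.52/35) = 0.234
- √((0.2211 + 0.2059)/35) = 0.110
- power = Φ[(0.38 − 0.234)/0.110] = Φ(1.32) = 90.7%

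The same formula gives 89.6% for 85% vs 50%. The 91% for the historical comparison also reproduces: 60% in 35 vs 34/117 as two samples gives 91.6% pooled and 91.1% by exact chi-square.

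**Step 2: use the section's own 60%.** For 60% vs 29%, n = 35, p̄ = 0.445:
- 1.96·√(2 × 0.445 × 0.555/35) = 0.233
- √((0.2400 + 0.2059)/35) = 0.113
- power = Φ[(0.31 − 0.233)/0.113] = Φ(0.68) = 75.3%

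By this formula 90% power at 60% vs 29% would need 52 per arm.

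**Step 3: exact power, chi-square (Fisher).**

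| PepCan vs Candin | 35 per arm | 40 per arm |
|---|---|---|
| 67% vs 29% (stated) | 89.4% (84.3%) | 94.5% (91.4%) |
| 85% vs 50% (stated) | 90.3% (85.2%) | 93.3% (89.8%) |
| 60% vs 29% | 73.9% (65.9%) | 82.3% (75.6%) |
| 60% vs 40% | 36.5% (28.0%) | 45.8% (36.9%) |
| 60% vs 50% | 12.2% (8.1%) | 15.7% (10.8%) |
| 67% vs 40% | 60.6% (51.3%) | 70.6% (62.3%) |
| 67% vs 50% | 29.3% (22.0%) | 35.1% (27.0%) |

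**Step 4: detectable difference.** With PepCan at 60% and 35 per arm, chi-square power is 79.8% against 27% (33 points) and 82.5% against 26% (34 points). Reaching 90% needs Candin at 22% (91.2%; at 23% it is 89.4%), which is below the 29% placebo rate.

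**The case against.** The claim in 1.5.9 is conditional. The rates are offered as examples, and the sentence begins by admitting uncertainty about Candin. The arithmetic is right for a chi-square-type test at 35 per arm, and with 40 per arm both scenarios come out at about 90% or more by either test. This stands: the section contains no computational error.

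The 60% is called conservative, and the section expects response to rise between 3 and 12 months. The interim Phase I rate at 50 µg per peptide was 83% (5 of 6), and section 1.5.8 cites a rise from 25% to 47% for a similar vaccine. Adding those 22 points to the Phase I overall rates of 45% to 52% (an assumption) gives 67% to 74%. At 74%, chi-square power with 35 per arm is 97% against 29% and 83% against 40%. This stands in part. A rate above 60% is possible, so 60% is not a ceiling. But the final Phase I rate at that dose was 50% (7 of 14). Phase I also counted absence of HSIL as complete response (section 1.4.1), whereas section 9.1 counts any remaining CIN as non-response, so Phase I rates may overstate the Phase II endpoint.

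Neither document says that a null result will be read as absence of a peptide effect, and SAP II.c provides Clopper-Pearson 95% intervals. That is fair, but no interval for the difference between arms is specified, and the power statement is what a reader would use to interpret a null.

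**Conclusion.** The concern holds as one of optimistic and inconsistent planning rates. At the section's own 60%, and with Candin no better than placebo, power is 74% by chi-square or 66% by Fisher at 35 per arm. That is about 15 points below the 89% that chi-square gives for the plan's 67% vs 29%. Separately, the Fisher test named in the protocol takes the two stated scenarios down to 84% and 85%. The lower figures, 37% (28%) at Candin 40% and 12% (8%) at Candin 50%, are a sensitivity range and rest on assumed Candin rates.

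Three stronger readings are tempting, and the documents do not support them:

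- **Power is at most 74%.** This treats a rate labelled conservative as an upper bound. It is also specific to 35 per arm and chi-square.
- **Power is probably below 40% on the plan's own rates.** The plan has no Candin planning rate. With PepCan at 60% and chi-square, this needs Candin at about 40% or more, and nothing in the documents makes that probable.
- **The Phase I rates of 44% and 57% in section 1.5.13 stand for Candin alone.** They are 3-month responses to PepCan by HPV type, so setting them against a 12-month PepCan rate mixes treatments and time points.

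Nor is Candin held at the placebo rate throughout: the second scenario gives it 50%.

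**What to change.** In Protocol section 1.5.9:

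- Replace the claim of at least 90% with a between-arm power table at PepCan 60% and 67% against Candin 29%, 40% and 50%, for the test finally chosen. Label the Candin rates as assumptions, and do not use 44% or 57% as Candin rates.
- State that with 35 per arm and PepCan at 60%, the smallest difference detectable with about 80% power is 33 to 34 points by chi-square. Recompute this if Fisher is kept.

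In 1.5.9 and in one sentence of SAP II.c, state that a non-significant PepCan vs Candin result will not be taken as showing that the peptides add nothing.

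The cost is a wording change and a less favourable stated power. The sample size, endpoint and procedures stay as they are.
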